
Study 3- Exploratory Analysis: Distributional characteristics will be assessed and outliers checked for accuracy. Prior to inferential procedures, standard descriptive statistics will be calculated for demographics, anthropometric and behavioral data, and data assessed for non-normality and transformation applied where appropriate. Analysis of Covariance (ANCOVA) will assess the group difference of father's weight after controlling for father's weight at baseline and potential covariates (father's education, household income and child gender), and group membership will be treated as the between subjects factor. Prior to conducting the ANCOVA, the homogeneity of regression assumption will be tested. This approach will also be used to assess the effect on children's BMI z-scores, and the father's and children's behaviors. Correlations of the father's and child's carotenoid intake as measured by the food frequency questionnaire will be compared to the average of the dermal carotenoid assessments at baseline as well as the correlation of the change of the reported and dermal assessments from T0-T1.

Feasibility Criteria for Study 3: Retention of subjects in study assessments 1. Retain 80% of intervention and control participants for pre- and post-assessments 2. Recruit 40 Latino fathers and their families in ≤ 4 months 3. Maintain ≥70% attendance to program sessions 4. The participating Latino fathers will be satisfied with the program as measured by 80% excellent-good satisfaction from questionnaires and exit interviews with the Latino fathers and their co-parent (typically children's mother). 5. Ability to collect anthropometric, behavioral and parenting data on at least 75% of the Latino fathers and anthropometric, and behavioral data on their children (both groups) at baseline and follow up

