#### Both Dads and Kids:

1. Demographics
2. Height, weight, and waist circumference as measured twice and averaged by trained research staff. If difference between the two initial measures are outside standard error, a third measure will be obtained.
3. Physical activity and sleep (as measured by wearing accelerometers for 5-7 days). Actigraph GT3X accelerometers will be used. Fathers and oldest child will be asked to wear accelerometers. If enough monitors are available, participating siblings will also be invited to wear the monitors. Fathers and children will be instructed in wearing their accelerometer and told to wear it 24 hours/day for the next 7 days, only taking it off when there is potential for getting it wet (e.g. bathing, showering, swimming). Study staff will remind the father and child to wear their monitor by text, email or phone call (depending on family preference) several times during week. Accelerometers and wear logs can be returned at the clinic or by prepaid envelope provided by the study. Once received back, accelerometer data will be reviewed for completeness (minimum of 8 hours/day for 5 days including 1 weekend days). If accelerometer data is not complete, the father and/or child will be encouraged (optional) to wear the monitor for additional days to complete the data.
4. Screen media use by survey questions

5. Dietary intake by age-appropriate Block food frequency questionnaire (2) on father and oldest participating child.
6. Dermal Carotenoid Assessment to assess dietary carotenoid intake. Carotenoids are nutrients we get from various fruits and vegetables. The Veggie Meter (Longevity Link, Corp., UT) is a portable electronic device that uses a small beam of light to measure skin carotenoid levels. Pressure-mediated reflectance spectroscopy will measure dermal carotenoid intensity. Before use, the device is calibrated. The same index finger of the participant is cleaned with an alcohol wipe and placed on the device's lens for 10 s at each visit. Triplicate readings are recorded electronically. This device does not diagnose or treat a disease or condition, so does not require FDA Investigational Device Exemption.
7. Program Satisfaction Survey at the end of the program

Mothers, if available, will be asked to assist the child in completing their questionnaires. If the family consists of a single father, he will assist the child in completing their questionnaires.

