After the 10 session program is completed for the intervention group, post-assessment data (T1) will be collected on all 40 families (intervention and wait-list control group) in the same way as described for the baseline data collection. In addition, fathers and mothers who took part in the Papás Saludables, Niños Saludables program will be asked to complete a satisfaction survey. Families who were assigned to the control group will start the program after the second data collection.

Exit interviews of all participating fathers, - mothers, and one child/family each who took part in the Papás Saludables, Niños Saludables program will be conducted. The interviews will be audio-recorded and coded for themes. The interview guides in English and Spanish are attached.

Process Evaluation: Attendance to the data collection sessions and Papás Saludables, Niños Saludables program sessions will be tracked by the program facilitators and research staff. Fidelity of program delivery will be assessed via research staff observation and use of a fidelity assessment tool (Attached in Section S for the Dads Facilitator and Kids Facilitator). This tool will also assess program content that worked well with Hispanic families and what did not go well, to allow us to continue to make improvements in the program. Families who stop attending the program will be contacted and asked for reasons/ barriers. If possible, staff will help trouble shoot to get them back in the program. Reasons for drop out or poor attendance will be recorded.

Families in the wait-list control will start the Papás Saludables, Niños Saludables program in the spring 2019. Exit interviews on these participants will be conducted at the end of the program. Father's and children's anthropometrics and father's HR and BP will be measured as per previous assessments. A voluntary non-paid invitation will be extended to these families to participate in short video interviews to create a promotional video.

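### Can the 80% satisfaction criterion be scored when exit interviews are coded for themes and the wait-list schedule lists no satisfaction survey?

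*Combined protocol and SAP*

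**What the plan says.** Section D makes satisfaction one of three measures of feasibility in Specific Aim 3, beside retention and engagement. Section G2 turns it into the fourth feasibility criterion: "The participating Latino fathers will be satisfied with the program", measured by "80% excellent-good satisfaction from questionnaires and exit interviews with the Latino fathers and their co-parent". It names no arm and no denominator, and gives no rule for combining the two sources.

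The Study 3 procedures (Section F.2 supplemental file) describe the data:

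- The assessment lists for dads and kids, and for dads and moms, each include a "Program Satisfaction Survey at the end of the program", with no restriction by arm. The text before these lists introduces them as assessments at baseline (T0) and after the intervention group's program (T1).
- At T1, fathers and mothers who took part in the program "will be asked to complete a satisfaction survey". Control families start the program after T1.
- On exit interviews: "The interviews will be audio-recorded and coded for themes".
- For wait-list families after their own program: "Exit interviews on these participants will be conducted at the end of the program". Anthropometrics are also taken, and the father's "HR and BP will be measured as per previous assessments". The satisfaction survey is not repeated there.

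**The concern.** Two things look wrong. First, a criterion expressed as a percentage draws partly on interviews whose only described processing is thematic coding. Themes do not give an excellent-good share, so one of the two named sources seems unable to contribute to the number it is meant to support.

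Second, the two sources appear to cover different fathers. Only the intervention group has had the program at T1, when the survey is given. The wait-list paragraph restates the interviews but not the survey. On that reading, wait-list fathers enter the criterion only through interviews that carry no rating, although the criterion speaks of participating fathers generally and both groups receive the program.

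At stake is whether a measure named in Specific Aim 3 has one reproducible scoring rule, or whether its pass or fail result could depend on a choice made after the data are seen.

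**Working it through.** The 80% is a chosen cut-off, so there is no derived figure to reproduce. The check sets the passages side by side and then sizes the ambiguity.

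**Sources.** The criterion names questionnaires and interviews. The questionnaire is a satisfaction survey given to fathers and mothers. The interviews are described only as recorded and theme-coded. The ordinary division of labour is that the survey gives the percentage and the interviews explain it. The survey and interview guides are attachments outside the reviewed text. A rating item in the guides is possible and cannot be checked.

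**Who is surveyed.** Two readings are open.

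- *Both arms.* The lists put the survey at the end of the program without naming an arm, and the T1 sentence covers those who took part, again without naming an arm. Wait-list fathers take part later and are covered.
- *Intervention arm only.* The lists are introduced as T0 and T1 assessments, and at T1 only the intervention group has finished. The survey is then an intervention-arm measure.

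Under either reading the lists and the T1 text agree with each other. They conflict only if the lists are read one way and the T1 text the other.

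**Size.** Inputs: 40 families (Section G1) and the 80% threshold (Section G2). Assumptions: 1:1 allocation, hence 20 fathers per arm, independent ratings, and equal satisfaction in both arms.

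The number needed is k = ceil(0.8 × n), so n = 20 gives 16 and n = 40 gives 32. Exact (Clopper-Pearson) 95% intervals at the threshold:

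- 16/20: 56.3% to 94.3%
- 32/40: 64.4% to 90.9%

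If 80% of fathers are rated, the counts are 13/16 (54.4% to 96.0%) and 26/32 (63.6% to 92.8%). This borrows the 80% retention target, which Section G2 sets for the pre- and post-assessments and not for the later wait-list contact.

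The chance of passing is P(X ≥ k) for X ~ Binomial(n, p). With A and B independent Binomial(20, p), the chance of opposite verdicts is P[(A ≥ 16) differs from (A + B ≥ 32)]:

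| True satisfaction p | Pass, n = 20 | Pass, n = 40 | Opposite verdicts |
|---|---|---|---|
| 60% | 5.1% | 0.6% | 4.8% |
| 70% | 23.8% | 11.1% | 18.1% |
| 75% | 41.5% | 30.0% | 24.3% |
| 80% | 63.0% | 59.3% | 23.3% |
| 85% | 83.0% | 86.5% | 14.1% |
| 90% | 95.7% | 98.5% | 4.1% |
| 95% | 99.7% | more than 99.9% | 0.3% |

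Disagreement is concentrated around the threshold, as it must be when 20 observations are compared with 40 that contain them. The table shows the effect of sample size. It shows no bias in either scoring.

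**Mixing the sources.** Suppose 15 of 20 surveyed fathers are positive (75%, a fail) and 20 wait-list interviews were classed as positive or negative and added. The combined share could lie anywhere from 15/40 = 37.5% to 35/40 = 87.5%, and would pass if at least 32 − 15 = 17 interviews were called positive. That spread needs a step the plan does not describe, namely converting themes into ratings. Thematic coding as written does not produce it.

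**The case for a change.** The strongest case for a change is that the criterion is the only satisfaction threshold for an aim that names satisfaction, and its scoring rule is incomplete. Neighbouring criteria name their groups (the first says intervention and control, the fifth says both groups), while this one does not. The procedures restate exit interviews for the wait-list families but not the survey, although both were first described for those who took part. That favours reading the omission as real, and then 20 of 40 fathers would have no questionnaire rating. The repair would cost one sentence and one existing short survey at a contact already planned.

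Much of this stands. The denominator, the combination rule and the wait-list survey are not stated clearly, and the arithmetic is right. But it shows missing detail, not a wrong result. Surveying intervention fathers at T1 and using wait-list interviews as qualitative feedback is a legitimate pilot design. Pooling the arms has its own cost: the result waits until the wait-list program ends, and the second group may receive a modified program, since the fidelity observations are meant "to allow us to continue to make improvements in the program". Moving co-parents out of the 80% would depart from a source the criterion names. Those are preferences between reasonable designs.

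**Conclusion.** The concern does not call for a change. The passages leave a detail open, and they do not contradict each other on any reading the text requires. The questionnaire gives the percentage, the interviews give the themes, and a competent analyst would report the share with its denominator, rater type and arm shown.

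The choice of arm matters moderately and only near the cut-off: opposite verdicts in roughly 14% to 24% of trials at true satisfaction of 70% to 85%, and under 5% at 60% or at 90% and above. These figures rest on 1:1 allocation, which the plan does not state, on equal satisfaction in both arms and on independent ratings.

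No passage ties the criterion to a go or no-go decision, no precision target is missed, and the planned questionnaire data are unaffected. If the unseen interview guides contain a rating item, some fathers would have two ratings. That would be a reporting matter and would not change this conclusion.

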## Section H: Potential Risks/Discomforts

### H1. Potential Risks/Discomforts

Describe and assess any potential risks/discomforts; (physical, psychological, social, legal, or other) and assess the likelihood and seriousness of such risks:

In Study One, fathers, mothers and children in the Panel of Latino Parents and Children are asked to provide input and feedback in order to culturally adapt the HDHK curriculum for the Latino population. There is minimal if any risk to the father or mother. There is a possible risk of loss of confidentiality, but all possible measures will be taken to minimize these risks (see section K).

Study Two, fathers are asked to participate in a secure internet survey over PA and food parenting practices. There is a possible risk of loss of confidentiality, but all possible measures will be taken to minimize these risks (see section K).

Study Three: Fathers, mothers and their children will participate in a healthy lifestyle program to promote national

guidelines for eating, physical activity and screen media use. Both fathers and children will be asked to participate in fun physical activity sessions, similar to PE class and there is a risk for injury. Facilitators will be trained in basic first-aid. Taking part in the physical activity sessions and doing the active games at home is considered minimal risk, because fathers and children can choose themselves the level of intensity and whether they participate.

The risks associated with assessments; Assessments are non-invasive procedures, that include heights, weights, waist circumference, blood pressure and heart rate measurements, and survey completion. Fathers and their children will also be asked to wear accelerometers at baseline and follow up. There are no known health risks or problems associated with wearing the activity (Actigraph GT3X) monitors. This activity monitor is commonly used to measure step counts and physical activity; and a similar monitors can now be found in cell phones and Fitbits that are publically available. There may be some embarrassment associated with wearing the Actigraph during the 7-day study period at baseline and follow up, but these are minimal risks. There is a possible risk of loss of confidentiality, but all possible measures will be taken to minimize these risks (see section K).

## H2. Data and safety monitoring plan

Do the study activities impart greater than minimal risk to subjects?

No

## H3. Coordination of information among sites for multi-site research

Is the BCM Principal Investigator acting as the SPONSOR-INVESTIGATOR for this multi-site research?

No or Not Applicable

Is BCM the COORDINATING CENTER for this multi-site research?

No or Not Applicable

## Section I: Potential Benefits

Describe potential benefit(s) to be gained by the individual subject as a result of participating in the planned work.

There will be no benefit to participate in study 1 or 2. Participants in study 3 may have benefit as the goal is to help them to increase their physical activity, improve their eating behaviors, and decrease their screen media to meet national guidelines. These behavior changes may improve their weight status. This program may also aid in targeting fathers to be more engaged, less permissive, and good role- models which can have a positive influence on children's lifestyle behaviors and weight status outcomes.

Describe potential benefit(s) to society of the planned work.

As HDHK had demonstrated significant, clinically relevant weight loss for participating fathers and significant behavior change for fathers and their children among Australian samples, we anticipate the potential for having similar clinically and significant outcomes for US Latino families. This would aid in reducing obesity- related medical conditions could benefit other Latinos in the future.

Do anticipated benefits outweigh potential risks? Discuss the risk-to-benefit ratio.

Given the potential impact on society in light of minimal risk to the participating parents and children, the benefits outweigh the risks.

## Section J: Consent Procedures

### J1. Waiver of Consent

Will any portion of this research require a waiver of consent and authorization?

Yes

Please describe the portion of the research for which a waiver is required. (Example: chart review to determine subject eligibility)

A waiver of full written consent and authorization will be required for fathers in Study 2, the cross-sectional study. The participant will be provided a cover letter for the secure internet survey (attached in section S), and consent will be obtained by clicking 'Yes' they wish to participate in survey.

Another waiver of full written consent and authorization will be required for the screening step of Fathers for study 3. A verbal consent for screening will be obtained and marked on the screening form.

Explain why the research and the use or disclosure of protected health information involves no more than minimal risk (including privacy risks) to the individuals.

Study 2: Parents will be reporting on their own use of parenting practices to support their child for healthy physical activity and eating behaviors, their co-parenting alliance and division of household labor. Demographics will be obtained to describe the study population and contact information to send the participants their compensation for participation, to verify

person is real to provide payment, and to re-contact a random sub-sample to take this survey again 2 weeks later.

Study 3: The father will self-report all the data so will be fully aware of the data we collect. The primary risk to screening is a loss of confidentiality, and we will follow procedures outlined in protocol to safe guard the data.

Explain why the waiver will not adversely affect the privacy rights and the welfare of the research subjects.

Study 2: Only survey data is collected and each participant can determine if they wish to voluntarily participate.

Study 3: The screening procedure will be explained to fathers and he will be given the right to opt out of screening and participation in the study.

Explain why the research could not practicably be conducted without the waiver and could not practicably be conducted without access to and use of the protected health information.

Study 2: Only survey data is collected and identifiers of participants are required for payment disbursement and to contact for the follow up study, therefore the risk is minimal but identifiable data is necessary.

Study 3: A waiver of consent is necessary because it will most frequently be done by phone. This means that getting a written consent would drastically limit the number of fathers screened because he would either need to provide written consent in person or by mail.

Describe how an adequate plan exists in order to protect identifiers from improper use and disclosure.

Study 2: The Electronic identifiable data will be stored on pass-word protected BCM servers which only the PI and study staff have access. The data for Study 2 will be collected by a secure version of Survey Gizmo. BCM has a business agreement with Survey Gizmo to keep data secure and delete the data after 12 months. Payment for study 2 will be issued via ClinCard following BCM standard procedures. No hardcopy identifiable data is anticipated for Study 2, other than reimbursement forms required by BCM for payment of participants. Copies of these will be kept in locked file cabinets behind locked doors in the CNRC.

Study 3: Screening will be done with the attached health screening form. Any identifiable data will only be on a) the screening form, which will be kept locked up in study file cabinets in the CNRC, a federal building with 24 hour security and access limited to key cars; or b) a study tracking database of enrolled participants stored on pass-word protected BCM servers which only the PI and study staff have access.

Describe how an adequate plan exists in order to destroy identifiers at the earliest opportunity consistent with conduct of the research, unless there is a health or research justification for retaining the identifiers or such retention is otherwise required by law.

Study 2 and 3: Contact information of participants will be destroyed once the study is complete.

Describe how adequate written assurances exist in order to ensure that the PHI will not be reused or disclosed to (shared with) any other person or entity, except as required by law, for authorized oversight of the research study, or for other research for which the use or disclosure of the PHI would be permitted under the Privacy Rule.

Study 2: The only health information collected in study 2 are self-reported weight and height. Identifiable self-reported behavior data will be collected and will only be shared as indicated in this protocol. Copies will be made available to NIH (our sponsor) if requested by them and participants will be notified of this in the survey cover letter.

Study 3: The screening data will only be used to assess inclusion/exclusion criteria for this study and report on the feasibility outcome of recruitment, screening and enrollment into the Feasibility Study. Any reports regarding the screening outcomes will be for summarized data (total numbers, lists of reasons for not qualifying, etc) and no identifiers will be reported in such reports.

Information from health records such as diagnoses, progress notes, medications, lab or radiology findings, etc.

No

Specific information concerning alcohol abuse:

No

Specific information concerning drug abuse:

No

Specific information concerning sickle cell anemia:

No

Specific information concerning HIV:

No

Specific information concerning psychiatry notes:

No

Demographic information (name, D.O.B., age, gender, race, etc.):

Yes

Full Social Security #:

No

Partial Social Security # (Last four digits):

No

Billing or financial records:

No

Photographs, videotapes, and/or audiotapes of you:

No

Other:

Yes, as described:

Self reported health information as per the ACSM health screener.

Will additional pertinent information be provided to subjects after participation?

Yes

If Yes, explain how subjects will be provided additional pertinent information after participation.

Study 3: Fathers will be told if they failed the health screener and instructed to see a medical provider for medical clearance in order to assess if it is safe for them to participate in the program.

